## Procedures

The duration of participation is limited to the two blood draws.

# **Data Analysis Procedure**

In the PACIFY trial, at 2 hours, patients receiving fentanyl had a PRU value of 113 +/- 94 on the platelet aggregation study (light aggregometry using ADP) after receiving Brilinta (ticagrelor), versus 71 +/- 66 in those not receiving fentanyl. With an alpha of 0.05 and beta of 0.8, 57 patients would be required to demonstrate statistical significance if there is a similar magnitude of effect. In the PERSEUS trial at 2 hours, patients receiving fentanyl had a PRU value of 173 +/-90 after also receiving Brilinta (ticagrelor), versus 210 +/- 76 in those receiving morphine and Brilinta (ticagrelor). 74 patients would be required to show statistical significance in direct comparison of morphine vs fentanyl. The aim is to enroll 80 patients in each arm (no narcotic, morphine, and fentanyl).

Two-tailed T-testing will be used to look for differences in the 2 hour platelet reactivity response rates between those receiving morphine versus those not receiving narcotics and between those receiving fentanyl and those not receiving narcotics.

If the data is sent to the Spectrum Health SASS team for analysis MRN's will be converted to a study ID so that the actual MRN will not be sent out.

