## Methodology

Given the challenges in obtaining a sufficient sample of patients with acute coronary syndrome (ACS) to prospectively compare fentanyl to morphine, the study will focus on chest pain patients in the emergency department. These patients typically have blood drawn initially and again two hours later to check for elevation and changes in troponin levels, a cardiac muscle protein detectable when cardiac muscle is being injured. These blood draws will be supplemented by evaluating platelet aggregation at the 0 and 2-hour marks.

There are many measures and techniques in evaluation of platelet function. Light Transmission Aggregometry (LTA) looks at changes in light transmittance through serum as platelets aggregate, leading to increased light transmission as more platelets aggregate. Aspirin interferes with arachidonic acid mediated aggregation because of its effects upon COX-1 conversion of arachidonic acid to thromboxane A2. Arachidonic acid is therefore the best trigger to use to evaluate aspirin's effect upon platelets, as opposed to epinephrine, ADP, or several others used to evaluate the stronger anti-platelet oral and IV agents that act in different places in the platelet activation cascade (8).

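### The arms are sized on PRU after ticagrelor, but the endpoint is arachidonic-acid aggregation after aspirin; the power label is wrong and one of the two sizing figures does not reproduce

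*Combined protocol and SAP*

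**What the plan says.** All sizing inputs are in the Data Analysis Procedure section. For fentanyl against no fentanyl, the first source trial (PACIFY) is reported as "patients receiving fentanyl had a PRU value of 113 +/- 94 on the platelet aggregation study (light aggregometry using ADP) after receiving Brilinta (ticagrelor"; its comparison arm, without the opioid, had 71 with an SD of 66. The error rates are given as "With an alpha of 0.05 and beta of 0.8", and the conclusion is that "57 patients would be required to demonstrate statistical significance if there is a similar magnitude of effect". For morphine against fentanyl, the second source trial (PERSEUS) is reported as "patients receiving fentanyl had a PRU value of 173 +/-90", also after ticagrelor, against 210 +/- 76 with morphine. From this the plan derives 74 patients, and it then sets a target of 80 in each of three arms.

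The endpoint is fixed elsewhere. Research Design adds arachidonic-acid aggregation to the 0 and 2 hour draws in patients given aspirin. Methodology calls arachidonic acid the best trigger for reading aspirin's effect, "as opposed to epinephrine, ADP, or several others used to evaluate the stronger anti-platelet oral and IV agents" that act elsewhere in the platelet cascade. The literature review says the authors know of no study of fentanyl and aspirin absorption.

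For the analysis, "Two-tailed T-testing will be used to look for differences in the 2 hour platelet reactivity response rates", comparing each opioid group with the no-narcotic group. No confidence interval is specified.

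**The concern.** The effect and the SD come from a different antiplatelet drug and a different readout from those this study will use. For the first source trial the plan names ADP, a trigger that its own Methodology section sets aside for aspirin. For the second it gives only PRU after ticagrelor and names no trigger. The sole link from those data to this endpoint is the condition that the effect be of similar magnitude.

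At stake is how the power statement will be read. A reader of a non-significant result would weigh it against 80% power, yet that figure was not derived for arachidonic-acid aggregation after aspirin, and the plan does not show how fast power falls if the effect there is smaller. Two further faults sit in the same paragraph. The error rate is mislabelled, and the second sample size is too small for its own inputs.

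**Working it through.** **Inputs** (Data Analysis Procedure)
- PACIFY: means 113 and 71, SDs 94 and 66. Difference 42; average SD (94 + 66)/2 = 80; root-mean-square SD √((94² + 66²)/2) = 81.2.
- PERSEUS: means 173 and 210, SDs 90 and 76. Difference 37; average SD 83; root-mean-square SD √((90² + 76²)/2) = 83.3.
- Two-sided alpha 0.05 and equal groups of 80.

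**Formula.** n per arm = 2 (z₁₋α/₂ + z_power)² SD² / difference².

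**Reproducing 57.** With power 0.80 and SD 80: 2 × (1.96 + 0.84)² × 80² / 42² = 56.95, so 57 per arm. The root-mean-square SD gives 59. The plan does not say whether 57 is per arm or in total; it reproduces only as per arm. One-sided testing, 90% power, or either single arm's SD does not give 57.

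**Taking beta 0.8 literally.** Power would be 0.20: 2 × (1.96 − 0.84)² × 80² / 42² = 9.1, so 10 per arm. The plan therefore means power 0.80, beta 0.20.

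**Trying to reproduce 74.** With power 0.80: average SD 83 gives 79 per arm, and root-mean-square SD 83.3 gives 80. The value 74 appears only with choices that contradict the plan's two-tailed test, for example one-sided with the larger SD of 90. At 74 per arm, power for this difference is about 77%. At 80 per arm it is about 80% (d = 37/83.3 = 0.444), which leaves no reserve.

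**What 80 per arm gives on any scale.** Detectable standardized difference at 80% power: (1.96 + 0.84) × √(2/80) = 0.443, or 0.446 with the t distribution. The documents give no SD for the aspirin readout. If it were 10, 20 or 30 aggregation units (assumed), the detectable difference would be 0.446 × SD = 4.5, 8.9 or 13.4 units.

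**Sensitivity to the borrowed effect.** PACIFY d = 42/81.2 = 0.517. The fractions below are an assumed range and are not in the documents. Power is from the t distribution; n is from the formula above.

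| Share of 0.517 | d | Power at 80 per arm | n per arm for 80% power |
|---|---|---|---|
| 100% | 0.517 | 90% | 59 |
| 75% | 0.388 | 68% | 105 |
| 50% | 0.259 | 37% | 235 |
| 25% | 0.129 | 13% | 940 |

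**The case against.** The plan is open about the assumption: the 57 is explicitly conditional on a similar effect, and the authors say that direct fentanyl–aspirin data are not known to them. It also has a rationale. The literature review argues that opioids slow gut transit and hence the absorption of oral drugs in general, with examples across several antiplatelet agents. Every sample-size calculation posits an effect. The 57 is arithmetically sound, and the beta label is a slip that did not alter N. All of this stands. It makes the borrowing understandable, but a shared mechanism does not supply a magnitude or an SD on another assay, and the plan shows no range.

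Three stronger readings are tempting, and the documents do not support them.
- A reader might infer that a null result could not be interpreted. That does not follow. A 95% confidence interval uses the SD observed in this study and shows which differences are excluded, wherever the planning inputs came from.
- A reader might take the gap between the two fentanyl-plus-ticagrelor arms, 113 against 173, as proof that the figures do not carry over. Those are absolute levels in two separate studies. Sizing uses within-study differences and SDs, and the average SDs are close (80 and 83).
- A reader might use the detectable difference as a margin for declaring no meaningful effect. The 0.446 SD is set by n = 80, not by relevance. The interval's half-width is about 1.96 × √(2/80) = 0.31 SD, so even with a true difference of zero the whole interval falls inside ±0.446 SD only about 60% of the time.

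**Conclusion.** The concern holds for the sizing statement; it is not a case against 80 per arm. The inputs describe another drug and readout, nothing in the plan connects them quantitatively to the aspirin endpoint, and 80% power is therefore assumed for that endpoint, not shown. What can be said without borrowing is that 80 per arm detects about 0.45 SD with 80% power per comparison. Whether an effect that large is plausible or relevant on arachidonic-acid aggregation cannot be judged from the documents. Power runs from about 90% down to 13% over the assumed range of 100% to 25% of 0.517 SD.

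Separately, beta 0.8 must be power 0.80, and 74 should be 79 to 80 on its own inputs. These results assume two-sided tests at 0.05 without multiplicity adjustment, and 80 patients with usable results in each group.

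**What to change.** In the Data Analysis Procedure section:
1. Correct the error rate to power 0.80 (beta 0.20), two-sided alpha 0.05, and say that sample sizes are per arm.
2. Replace the sizing claim with wording such as: *80 per arm gives 80% power (two-sided alpha 0.05, per comparison) for a difference of about 0.45 SD in 2-hour arachidonic-acid aggregation.*
3. Keep the two ticagrelor trials as background. If their sample sizes are still shown, correct 74 to 79 or 80 and name the SD convention used.
4. Show power over an assumed range of effects: about 90%, 68%, 37% and 13% at 100%, 75%, 50% and 25% of 0.517 SD.
5. Report each contrast with its 95% confidence interval in aggregation units, and state that non-significance will not be read as absence of effect. Do not use the detectable difference as an equivalence margin.

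The cost is rewording and interval reporting, with no extra patients, blood draws or tests. The downside is that the stated power becomes less flattering.

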# Introduction or Background

#### Problem and Purpose Statement-Objective of the Research

The aim of this project was to determine whether fentanyl and morphine have similar effects in reducing aspirin's effect upon platelets in emergency department patients with chest discomfort. Morphine has been shown to worsen outcomes in heart attack patients due to reduction of oral anti-platelet agent effectiveness and so many providers have switched to using fentanyl. However, it is largely unknown whether fentanyl has similar effects.

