### Theoretical Framework-Present Knowledge, Literature Review

Patients experiencing heart attacks or unstable angina (commonly known as acute coronary syndrome (ACS)) commonly experience discomfort and pain. Nitroglycerin is typically the first medicine given for discomfort because it has dilatory effects upon vasculature to reduce the blood pressure and relax blood vessels to decrease myocardial demand. However, in some patients it is contraindicated and in many patients it is only partially efficacious in reducing discomfort. Narcotics are commonly given. Classically morphine was given in ACS as it is also thought to have venodilatory properties and could perhaps also relax the patient to decrease the sympathetic demands of the frightfight-flight responses experienced by patients having heart attacks. Narcotics have several common side effects, and one of these is decreased gastrointestinal (GI) transit time, commonly manifested as constipation. However, this decreased GI transit time also can slow the absorption of oral medications. Oral anti-platelet therapy (starting with aspirin and commonly including dual anti-platelet therapy with clopidogrel as well) is also part of the treatment of patients with ACS as reducing clot propagation in the coronary arteries can decrease the size of an infarct. Interference with oral anti-platelet therapy has been observed with morphine (2) contributing to worse outcomes in patients receiving morphine (1). Delayed onset of action or decreased absorption has also been demonstrated with stronger anti-platelet drugs such as clopidogrel (3) and prasugrel (4) in association with morphine. Many physicians have therefore switched to using fentanyl, and fentanyl has been found to be equally efficacious in pain control in potential ACS (7). The PACIFY trial (5) evaluated the effects of fentanyl upon the stronger anti-platelet agent ticagrelor and found statistical significance at 2 hours with a lower peak concentration, and delayed onset of the peak concentration of ticagrelor when fentanyl was given. The PACIFY trial did not compare the effects of morphine to fentanyl. The PERSEUS trial was a small study of 38 patients (6) which showed no difference between fentanyl and morphine at 2 hours with regards to ticagrelor absorption but that there was a difference at 4 hours. There has not to our knowledge been any study of fentanyl's effect on aspirin absorption.

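### The 74 patients stated for morphine vs fentanyl does not follow from the PERSEUS values printed beside it; the method that reproduces the plan's 57 gives 79 per group with the PERSEUS SDs.

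*Combined protocol and SAP*

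**What the plan says.** The combined protocol and SAP justifies its size under Data Analysis Procedure with two calculations.

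- **Fentanyl vs no fentanyl, from PACIFY:** 113 +/- 94 against 71 +/- 66. The plan then states: "With an alpha of 0.05 and beta of 0.8, 57 patients would be required".
- **Morphine vs fentanyl, from PERSEUS:** the values are "173 +/-90 after also receiving Brilinta (ticagrelor), versus 210 +/- 76", and the plan concludes that "74 patients would be required to show statistical significance in direct comparison of morphine vs fentanyl".

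No separate alpha, power, SD or sidedness is given for the second calculation. No formula is shown, neither figure is labelled per group or total, and no allowance for loss is stated. The paragraph ends: "The aim is to enroll 80 patients in each arm". Sample/Participants repeats that target. For the analysis, "Two-tailed T-testing will be used to look for differences", and the two comparisons named are each narcotic against no narcotic.

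**The concern.** The two sample sizes stand side by side, and alpha and power are stated once, so a reader expects one method behind both. The first figure can be reproduced from its printed inputs. The second cannot be reproduced from its own inputs by that method.

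The 74 is the larger of the two figures and comes directly before the target of 80 per arm. Together they look like a requirement of 74 with six patients per arm in hand. If the PERSEUS SDs are the intended inputs, nearly all of that apparent reserve goes. The comparison matters to the stated aim, which is "to determine whether fentanyl and morphine have similar effects".

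**Working it through.** **Inputs (all from Data Analysis Procedure)**
- PACIFY: difference 113 - 71 = 42; SDs 94 and 66, mean (94 + 66)/2 = 80.
- PERSEUS: difference 210 - 173 = 37; SDs 90 and 76, mean (90 + 76)/2 = 83.
- Alpha 0.05, taken as two-sided because the planned tests are two-tailed.
- Power 0.8. The plan prints this as beta, but a beta of 0.8 would mean 20% power, and 57 is reproduced with power 0.8.

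**Formula.** n per group = 2 x (1.960 + 0.842)^2 x SD^2 / d^2, with (1.960 + 0.842)^2 = 7.849.

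**Step 1: the plan's own 57.** 2 x 7.849 x 80^2 / 42^2 = 56.95, so 57. The match is exact and supports the per-group reading. Read as a total (28.5 per group), 57 would give only about 51% power.

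**Step 2: the same method on PERSEUS.** 2 x 7.849 x 83^2 / 37^2 = 78.99, so 79, against the printed 74.

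**Step 3: other standard two-sided methods using both SDs (per group)**

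| Method | PACIFY | PERSEUS |
|---|---|---|
| Mean SD, normal | 57 | 79 |
| Mean SD, t-test | 58 | 80 |
| Root-mean-square SD (81.22; 83.29), normal | 59 | 80 |
| Root-mean-square SD, t-test (Welch the same) | 60 | 81 |

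The printed 74 is therefore 5 to 7 per group too low for the PERSEUS inputs.

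**Step 4: where 74 could come from**
- *Difference 37 with SD 80, the PACIFY mean SD:* 2 x 7.849 x 80^2 / 37^2 = 73.39, so 74.
- *One-sided test with SD 90 alone:* 2 x (1.645 + 0.842)^2 x 90^2 / 37^2 = 73.16, so 74. This conflicts with the two-tailed plan and ignores the printed SD of 76. The matching PACIFY calculation (one-sided, SD 94) gives 61.94, so 62, not 57.
- *Power lowered to 0.77, mean SD 83:* 74, but PACIFY then gives 53, not 57.
- *74 as a total (37 per group):* about 48% power with mean SD 83.

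Of the routes tried, only the first gives both 57 and 74, and it does not use the PERSEUS SDs.

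**Step 5: power.** By the normal formula, power = Phi(d / (SD x sqrt(2/n)) - 1.960).
- Morphine vs fentanyl, n = 74, SD 83: 37 / 13.645 - 1.960 = 0.752, so 77.4%. Across the methods in Step 3: 76.5 to 77.4%.
- Morphine vs fentanyl, n = 80, SD 83: 37 / 13.123 - 1.960 = 0.859, so 80.5%. Across methods: 79.7 to 80.5%.
- Fentanyl vs no narcotic, n = 80, PACIFY inputs: 90.1 to 91.3% across methods.

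**The case against.** The strongest reply is that one formula does give both printed figures. With a common SD of 80, a difference of 42 gives 57 and a difference of 37 gives 74. If that SD was chosen deliberately, 74 is correct for it, and power by the normal formula is 80.3% at 74 and 83.3% at 80. This stands as far as it goes: the plan does not say which SD lies behind 74. It also never mentions a common SD, and it prints the PERSEUS SDs as part of the values that lead to 74. Even on this reading the text needs correcting, because the SD used is unstated and differs from those shown.

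A second reply is that the correction is small beside the uncertainty of its inputs. The plan itself notes that "The PERSEUS trial was a small study of 38 patients". Assuming an even split of 19 per group, the standard error of the difference of 37 is sqrt((90^2 + 76^2)/19), about 27. The inputs are also ticagrelor data, whereas this study measures arachidonic-acid aggregation after aspirin. All of this stands and limits the importance of the point. It does not make 74 follow from the printed values.

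A reader might infer that no calculation on the PERSEUS values can reach 74. That is too strong: the one-sided route with SD 90 alone reaches it, although it conflicts with the two-tailed plan and fails on PACIFY.

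**Conclusion.** The point holds as a minor internal inconsistency. With the PERSEUS SDs, the method that reproduces 57 gives 79 per group, not 74, and the other standard methods give 80 or 81. The apparent reserve of six per arm (80 - 74) becomes one (80 - 79) or none.

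This rests on reading +/- as SD, both sizes as per group, and alpha and power as carried over to the second calculation. The exact match to 57 supports these readings, but the plan does not state them. A carried-over PACIFY SD is the likely source of 74; with no working shown, that remains an inference.

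Two stronger conclusions are tempting. A reader might infer that the study is undersized for morphine vs fentanyl. The documents do not support that: the operative target is 80 per arm, which gives about 80% power on the PERSEUS inputs, and this comparison is not among the listed t-tests. A reader might also infer that the plan claims a reserve it lacks. The plan claims none; the reserve is only suggested by the two numbers standing together, and its loss depends on the PERSEUS SDs applying.

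**What to change.** Under Data Analysis Procedure:

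1. Replace 74 with 79.
2. Write 'per group' after both 57 and 79.
3. Name the method once for both figures: mean of the two SDs, normal formula, two-sided alpha 0.05.
4. Change the beta wording to 'power 0.8 (beta 0.2)'.
5. Add: *If the PACIFY and PERSEUS differences and SDs apply, 80 evaluable patients per arm gives about 80% power for morphine vs fentanyl, with essentially no reserve, and about 90% for fentanyl vs no narcotic.*

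The condition in item 5 is needed because both sets of inputs come from ticagrelor studies. The change is wording only: no extra patients and no change to procedures. Its one downside is a slightly less favourable stated margin.

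### The plan asks whether fentanyl and morphine act alike on aspirin's effect, but it lists no head-to-head analysis and no criterion by which similarity could be shown

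*Combined protocol and SAP*

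**What the plan says.** - **Aim.** Problem and Purpose Statement sets out to "determine whether fentanyl and morphine have similar effects" in blunting aspirin. Research Questions or Hypothesis adds that both drugs are expected to reduce aspirin's effectiveness.
- **Sizing of the direct comparison.** Data Analysis Procedure takes 2-hour results from a head-to-head ticagrelor trial (PERSEUS): "patients receiving fentanyl had a PRU value of 173 +/-90 after also receiving Brilinta (ticagrelor), versus 210 +/- 76 in those receiving morphine". From these it concludes that "74 patients would be required to show statistical significance in direct comparison of morphine vs fentanyl". The target is 80 in each of three arms.
- **Planned tests.** "Two-tailed T-testing will be used to look for differences in the 2 hour platelet reactivity response rates", and the sentence goes on to name two pairs: morphine against no narcotic, and fentanyl against no narcotic. Morphine against fentanyl is not named. No interval, margin or rule for reading a non-significant result appears anywhere.
- **Background on the same source.** The literature review says "The PERSEUS trial was a small study of 38 patients", and that it "showed no difference between fentanyl and morphine at 2 hours with regards to ticagrelor absorption but that there was a difference at 4 hours".
- **Measurement.** Methodology specifies light transmission aggregometry triggered by arachidonic acid, at 0 and 2 hours only.

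**The concern.** A question about similarity needs an estimate of the difference between the two drugs and a statement of how large a difference would still count as similar. The plan provides neither. It provides a sample size for finding a difference and two tests that answer another question, namely whether each opioid differs from none.

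Two results could be misread as similarity. Both opioids might differ significantly from no narcotic, although their effects could be of quite different size. Or an unlisted head-to-head test might be non-significant, which shows only that a difference was not detected. The introduction says many providers have already moved from morphine to fentanyl, so an unsupported similarity statement, or an unsupported statement that they differ, would bear on current practice.

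The planning difference behind the 74 is also weak. It comes from a small trial, with another antiplatelet drug and another assay trigger.

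**Working it through.** **Inputs (Data Analysis Procedure unless stated).** Two-sided alpha 0.05. The "With an alpha of 0.05 and beta of 0.8, 57 patients would be required" sentence is read as power 0.80, and the same settings are assumed for the second calculation. Fentanyl 173, SD 90; morphine 210, SD 76; target 80 per arm. The source trial's 38 patients come from the literature review. Their split is not given, so 19/19 is assumed.

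**1. The plan's own figures.** Per arm, n = 2 × [SD × (1.960 + 0.842) / difference]².
- Fentanyl against none: difference 113 - 71 = 42, average SD (94 + 66)/2 = 80. n = 2 × (80 × 2.802/42)² = 57. This matches, so the stated figures are per arm.
- Morphine against fentanyl: difference 210 - 173 = 37, SD = √[(90² + 76²)/2] = 83.3. n = 2 × (83.3 × 2.802/37)² = 80, or 79 with the average SD of 83. The stated 74 does not reproduce. It would follow if the SD of 80 from the other trial were carried over: 2 × (80 × 2.802/37)² = 73.4, rounded up to 74. Power is 77% at 74 per arm and 80% at 80 per arm, so the enrolment target absorbs the slip.

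**2. Precision of the planning difference.** SE = √(90²/19 + 76²/19) = 27.0; t = 37/27.0 = 1.37 on 36 df; p = 0.18. The 95% CI is 37 ± 2.028 × 27.0, about -18 to +92. Splits as uneven as 25/13 or 13/25 give p between 0.18 and 0.21, and the interval always includes zero.

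**3. Power of 80 per arm (t-based, two-sided).** In SD units the planning effect is 37/83.3 = 0.44.

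| True 2-hour difference | SD units | Power |
|---|---|---|
| 37 | 0.44 | 80% |
| 30 | 0.36 | 62% |
| 20 | 0.24 | 33% |

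**4. What a non-significant result would leave open.** SE at 80 per arm = 83.3 × √(2/80) = 13.2, so the 95% half-width is 1.975 × 13.2 = 26. An observed difference of 25 would be non-significant, with interval 25 ± 26, or -1 to +51. That interval includes zero, 37 and values well above 37.

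**5. Whether 80 per arm could support a similarity claim.** The plan states no margin. As an illustration, take the plan's own effect of 37 units (0.44 SD).
- 95% interval: the observed difference must lie within 37 - 26 = 11 units of zero. If the true difference is zero, the chance is 2Φ(11.0/13.2) - 1, about 60%.
- 90% interval (half-width 21.8): the limit is 37 - 21.8 = 15.2 units. The chance is 2Φ(15.2/13.2) - 1, about 75%.

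These figures assume complete data, equal arms and an unadjusted comparison.

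**The case against.** The strongest reply is that the plan commits to less than the concern supposes. The listed tests match the hypothesis that both opioids reduce aspirin's effect, they are already confined to 2 hours, and no sentence says that a non-significant head-to-head result would be reported as similarity. That is fair, and misreporting is not shown. But the aim is still worded as similarity and the direct comparison is sized, so the plan leaves that question without an analysis.

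A reader might go further and infer four things that the documents do not support.

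- *The background contradicts the sizing.* The literature review's finding of no 2-hour difference concerns ticagrelor absorption, whereas the sizing uses a platelet-reactivity value. These are different measures and do not strictly conflict.
- *The 80% power is unsupported.* A non-significant estimate from 38 patients is imprecise, not refuted. Its interval also allows differences well above 37, and 80 per arm does give about 80% power at 37.
- *A null result is likely.* That would hold only if the true 2-hour difference were well below 37, which nothing in the documents establishes.
- *The lack of a 4-hour sample is a defect.* The 4-hour separation is a ticagrelor finding. The protocol knows of no study of fentanyl and aspirin absorption, and Methodology explains that the draws accompany the existing troponin draws.

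An objection to the remedy also stands in part. Using 0.44 SD as a similarity margin is a convenience and has no clinical justification in the documents.

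**Conclusion.** The concern holds in a limited form. As written, the plan cannot support a conclusion that the two opioids act similarly: the direct comparison is sized for significance but not listed as an analysis, and there is no interval or margin. With 80 per arm, a non-significant difference can coexist with an effect as large as the one planned for, because the 95% half-width is about 26 units against a planning effect of 37.

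The weakness of the 37-unit value is secondary. It is imprecise (p about 0.18, assuming 19 per group) and transfers from ticagrelor reactivity to arachidonic-acid aggregation after aspirin only if the standardised effect, 0.44 SD, is assumed to carry over. That calls for a caveat and a range. It does not invalidate the sample size, and the gap between 74 and about 80 is covered by the enrolment target. This is a wording-level improvement, and it leaves the design unchanged.

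**What to change.** Amend Data Analysis Procedure in four places.

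1. **Add the analysis.** Estimate the 2-hour morphine-minus-fentanyl difference in arachidonic-acid aggregation and report it with its confidence interval.
2. **State how a non-significant difference is read.** It is inconclusive and is not evidence of similarity.
3. **Set a similarity criterion.** Allow the conclusion that the drugs are similar at 2 hours only if the interval lies wholly within a pre-stated margin in SD units of the aspirin assay. The plan's own 0.44 SD is one example. The team should justify the margin, say which SD defines it, and fix the interval level (90% or 95%) in advance.
4. **Replace the 74-patient sentence.** Suggested text: *With 80 patients per arm and two-sided alpha 0.05, power for the morphine-fentanyl comparison is about 80% for a true difference of 0.44 SD, 62% for 0.36 SD and 33% for 0.24 SD. The 0.44 SD value comes from a 38-patient ticagrelor trial, is imprecise, and may not apply to aspirin.*

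No added patients or blood draws are needed. The cost is a narrower claim and a less favourable power statement. The plan should also disclose that, if the drugs are truly identical, the 0.44 SD criterion would be met only about 60% of the time with a 95% interval, or 75% with a 90% interval. A tighter margin would lower both figures.
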